- |€ The intervention will require heart rate monitoring utilizing a â€œPolar H10â€¢ heart rate monitor, with the goal of reaching moderate to high intensity for 30 minutes during the one hour long therapy intervention. A screenshot of the Polar heart rate data will be taken after each session of monitoring and sent to the PI where it will be collected and kept in a private folder on a locked computer, with all patient information such as patient name transcribed to

a number [REDACTED] for confidentiality. The screenshots themselves will be off of the Polar heart rate app on the primary therapistâ€™s phone but will contain no patient identifiers. Once the screenshots are taken, they will immediately be sent to the researcher and then within 24 hours they will be uploaded to a folder as mentioned above in order to ensure no data is lost. To the right is an example of what a screenshot would look like (note no patient identifiers). In order to send this information to the primary investigator, this photo will be sent via a Secure e-mail with the picture of the heart rate data in addition to the date this data was collected and the patient that this data was collected for. Once the e-mail is sent, the screenshot will be deleted from the therapistâ€™s phone. The PI will then store this information on a locked computer as noted above.

- Link to product: <https://www.polar.com/us-en/sensors/h10-heart-rate-sensor?sku=92075957>
- Instructions for use: <https://www.youtube.com/watch?v=oN-RchX1UEQ>

|€ The treatment intervention will consist of overground walking, treadmill walking (with or without bodyweight support), stairs, resisted walking, and all other stepping/ gait training. The goal of treatment will be to increase the intensity of the exercise safely and to patient tolerance.

|€ For safety, patient blood pressure will be monitored before and after each session at the very least. In patients with history of hypertension, stroke, or orthostatic hypotension, it may be taken several times throughout the intervention. Additionally, the following will all merit the intervention to be stopped:

- A drop in systolic blood pressure >20 mmHg with the increasing workload
- An increase in systolic and/or diastolic blood pressure >180 mmHg or 110 mmHg, respectively.
- Reported chest or arm pain (angina)

- Severe shortness of breath, cyanosis, pallor, lightheadedness, dizziness or confusion

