### **Data and Safety Monitoring**

|€ For subjects who were not physically active prior to their neurologic injury, with intense exercise there is a possibility for increase in cardiovascular events such as stroke or heart attack.

|€ Patients with premorbid conditions will have close blood pressure and heart rate monitoring throughout the session by a skilled Doctor of Physical Therapy. There are physicians on site at TIRR Memorial Hermann in addition to skilled therapists that understand signs of poor exercise tolerance such as pallor, profuse sweating, headache, and lightheadedness. Patients with chest pain at any point during the study will have exercise immediately discontinued and will have all of their vitals signs including blood pressure, heart rate, and oxygen saturation checked on the spot. There are blood pressure cuffs and oxygen saturation monitors throughout all of the gyms and in all of the units at TIRR Memorial Hermann and TIRR Kirby Glenn.

|€ However, in the neurologic population that will be receiving the intervention, there is greater risk associated with remaining sedentary. Patients who do not receive intensive rehabilitation are at greater risk for pressure injury, deep vein thrombosis, Type 2 Diabetes, and obesity. Additionally, sedentary individuals are more likely to have low cardiorespiratory fitness, which is a well-known risk factor for chronic diseases.

|€ Additionally, literature published by the American Heart Association and the Neurologic Physical Therapy Association supports the implementation of high-intensity stepping training. Hornby et al has provided extensive research of high intensity stepping training on patients with stroke. Even though these patients have already had a cardiovascular-related event, even with interventions in which they are required to maintain their heart rate at 75-85% of HR Maximum, there were no increases in adverse events.

|€ Since this population will also be engaging in stepping training and locomotor training, there could be potential for increased risk of falls during interventions. However, therapists at the Memorial Hermann facility (which is where the study will be conducted) are highly experienced in walking interventions for these patients and in the prevention of falls. Additionally, most high intensity training stepping in patients with stroke, TBI, and SCI is proven to improve balance and thereby decrease risk of falls.

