|€ For the more medically complex patients at TIRR inpatient (ie multiple comorbidities), a thorough chart review will be performed to ensure patient is not at increased risk of cardiovascular events (previous heart attacks, uncontrolled hypertension, etc). The Physical

Medicine and Rehabilitation Physician will also be asked to clear the patient for participation in high intensity training. For patients at Kirby Glenn outpatient, a chart review and medication review will be performed. If patient is at additional risk for cardiovascular event as determined by previous cardiac event or by uncontrolled hypertension as demonstrated by systolic blood pressure over 180 or diastolic blood pressure over 100 consistently, then the patient primary physician will be contacted to ensure the safety of high intensity training. Additionally, blood pressure and heart rate will be obtained before and after the intervention for every session. If patient has any signs of headache, nausea, vomiting, dizziness, blurred vision, double vision, or dysarthria during the treatment intervention, the treatment will be stopped immediately and vitals including blood pressure and heart rate will be taken.

- |€ In order to minimize fall risk, there will be a Doctor of Physical Therapy supervising the patient throughout the entire intervention. If the Doctor of Physical Therapy needs to leave even to get a blood pressure machine or a towel, the patient will take a seated rest break. -If any unplanned adverse events occur, or if protocol deviations occur, the PI of the study ([name]) will report these via the iRIS portal.
- |€ The PI of this study ([name]) will be responsible for reporting Serious Adverse Events and Unanticipated Problems to the IRB. The PI will also be responsible for maintaining the confidentiality of data, data collection, management, and analyses. The Primary Investigator will perform reviews of all data once every two weeks in order to ensure safety for all patients and to ensure all data is being tracked accurately.

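### The systolic-drop stop rule needs a blood pressure reading under load, but the minimum set for every patient is one reading before and one after each session

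*Combined protocol and SAP*

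**What the plan says.** Study Procedures lists findings that end the intervention. One is "A drop in systolic blood pressure >20 mmHg with the increasing workload". Another is a systolic pressure above 180 mmHg or a diastolic pressure above 110 mmHg. The remaining lines are symptoms and visible signs.

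The reading schedule for all patients is in the same section: "For safety, patient blood pressure will be monitored before and after each session at the very least". Data and Safety Monitoring repeats it: "blood pressure and heart rate will be obtained before and after the intervention for every session". Study Procedures asks the therapist to enter the before and after vitals in the note and names no others.

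Two sentences go further for some patients:

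- Study Procedures: "In patients with history of hypertension, stroke, or orthostatic hypotension, it may be taken several times throughout the intervention".
- Data and Safety Monitoring: "Patients with premorbid conditions will have close blood pressure and heart rate monitoring throughout the session".

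Neither gives an interval, and premorbid conditions are not defined.

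When a symptom occurs, the response is clear. "Patients with chest pain at any point during the study will have exercise immediately discontinued and will have all of their vitals signs" checked on the spot. A second symptom list in Data and Safety Monitoring also requires an immediate stop with blood pressure and heart rate taken.

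The planned dose is 30 minutes of stepping, three times a week for 3 weeks, which makes 9 sessions.

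**The concern.** A stop rule protects a patient only if the observation that triggers it is made. The systolic-drop rule applies to everyone, but the readings it depends on are not required of everyone. A reading before exercise has no workload behind it, and a reading afterwards comes when the workload has gone and there is nothing left to stop.

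What is at stake is safety, not inference: no planned analysis uses these readings. The plan takes cardiovascular risk seriously: "For subjects who were not physically active prior to their neurologic injury, with intense exercise there is a possibility for increase in cardiovascular events". A fall in pressure under rising load without symptoms is what this rule adds to the symptom stops, and it is what the minimum schedule cannot show.

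A second, smaller gap concerns what follows a stop. The plan does not say whether readings become more frequent in the next session, or who agrees that there should be one.

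**Working it through.** The plan gives no figure to reproduce. The check sets the reading requirements against the blood pressure stop rules.

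**1. What each patient group must have during stepping**

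| Group | Source | In-session reading | Interval |
|---|---|---|---|
| Every patient | Study Procedures; Data and Safety Monitoring | Permitted, not required | None |
| History of hypertension, stroke or orthostatic hypotension | Study Procedures | Optional (may) | None |
| Premorbid conditions (undefined) | Data and Safety Monitoring | Required (will) | None |

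A patient with one of the three histories may also count as having a premorbid condition, and would then come under the firmer sentence. Study Population admits degenerative disease, TBI, posterior fossa tumor and MS as well as stroke, so a patient with none of the three histories can be enrolled.

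**2. What each blood pressure rule can detect on the minimum schedule**

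- *Fall of more than 20 mmHg with rising workload.* This needs a reading while workload rises. The minimum schedule supplies none, so the rule cannot be triggered by required readings.
- *Above 180 or 110 mmHg.* The reading beforehand can stop a session from starting, and the reading afterwards can show a pressure that is still high. A peak that occurs and settles within the session is missed.

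**3. The floor, for a patient outside the groups with extra readings**

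- Required readings: 2 per session × 9 sessions = 18.
- Stepping time: 9 × 30 minutes = 270 minutes.
- Required readings within those 270 minutes: 0.

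This is what the plan requires, not a forecast of practice.

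**4. After a stop**

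Vitals at the stop are mandatory for chest pain and for the second symptom list. No sentence then changes the reading schedule for later sessions. The physician steps in Data and Safety Monitoring are clearance of medically complex inpatients and contact with the primary physician of outpatients at added cardiovascular risk. They follow from chart or medication review and are not expressly tied to a stop during training. If a stop came in session 1, 9 − 1 = 8 sessions (8 × 30 = 240 minutes) would remain on the same stated minimum.

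**5. Cost of two in-session readings**

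- Per patient: 2 × 9 = 18 extra readings. For 15 patients: 18 × 15 = 270.
- Assuming 1 to 2 minutes a reading: 2 to 4 minutes a session. Against 30 stepping minutes, 2/30 = 7% and 4/30 = 13%.

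**The case against.** The best defence is that the plan sets a floor, and the people applying it are skilled. A Doctor of Physical Therapy supervises throughout, heart rate is monitored during the session, cuffs are placed throughout the gyms, and physicians are on site at TIRR Memorial Hermann. Patients who cannot train for cardiac reasons are excluded. The investigator reports adverse events, reviews the data every two weeks and audits weekly. All this stands, and it means that a stop is unlikely to pass unnoticed. It does not supply the missing reading: heart rate does not show a fall in pressure, an available cuff is not a required measurement, and a record holding only before and after vitals cannot show whether the rule was checked.

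A reader might infer more than the documents support:

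- *That many patients go unmonitored.* The documents give no share of the 15 with a relevant history, and premorbid conditions may be meant broadly. The remainder could be few.
- *That the previously inactive patients named as at risk are left out of close monitoring.* The risk sentence is followed directly by the monitoring sentence. The two can be read as risk and mitigation, with inactivity among the conditions meant. The fair criticism is the missing definition.
- *That a cuff is not at hand.* The words "If the Doctor of Physical Therapy needs to leave even to get a blood pressure machine or a towel" belong to an instruction about preventing falls. If anything, they suggest that readings are taken mid-session.
- *That the blood pressure rules are idle altogether.* The 180/110 limit can act on the required readings, and only its in-session part is lost.

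**Conclusion.** The point holds in a limited form. For a patient outside the premorbid-conditions group, full compliance with the text can leave the systolic-drop rule without a single reading to act on. For the three named histories, readings under load are only optional unless the history also counts as a premorbid condition. A fall without symptoms, or a rise above 180/110 mmHg confined to exercise, could go undetected. The number of patients exposed and the event rate are not in the documents, so the expected harm cannot be sized.

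The conclusion assumes that the two attachments not supplied, the Study Schedule and the Case Report Form, do not already require in-session readings. If either does, the main point falls. They could likewise hold a step for resuming after a stop.

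This is a cheap safety improvement. The question of who agrees to resume is a secondary clarification and would not carry the point alone.

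**What to change.** In Study Procedures, add: *In every patient blood pressure is also taken at least twice during stepping, once after intensity is first raised and once near the end while the patient is working at or near the highest intensity reached.* This wording does not depend on a planned workload schedule, which the protocol does not have. Record these readings in the note beside the before and after vitals.

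In the sentence on hypertension, stroke and orthostatic hypotension, keep the three histories and change *may be taken several times* to *will be taken several times*. Keep the closer monitoring in Data and Safety Monitoring, and define premorbid conditions there.

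As a secondary clarification, add after the stop list: *After a stop for a blood pressure limit, chest or arm pain, or other serious signs, the rehabilitation physician (inpatient) or primary physician (outpatient) agrees before the next session, and in-session readings are repeated more often in that session.*

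The cost is a few sentences and, for 15 patients, 270 extra readings with equipment already in place. Stepping pauses for about 2 to 4 of the 30 minutes on the assumed reading time, and heart rate may dip during the pauses. A session may occasionally wait for a physician's agreement, more likely for outpatients.

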## Study Design

|€ The study will be a non-blinded prospective case series performed at TIRR Memorial Hermann and TIRR Kirby Glenn. Participants will be recruited if they have an ICD-10 code of ataxia or present with ataxia at initial evaluation. Either the director of the brain injury rehabilitation team or the evaluating therapist will contact the principal investigator in order to refer the patient to the study. The evaluating therapist will provide the PI with the referral through a secure e-mail utilizing their Memorial Hermann e-mail. The secure e-mail will include the patient diagnosis and their room number with no other personal identifiers listed until the patient consents to the research study.

|€ The study sample will be about 15 and the expected duration of the study will be at least 3-4 weeks.

|€ The primary outcomes measured include the 10 Meter Walk Test and the 6 Minute Walk Test. These outcome measures will be performed once at baseline and again at week 3.

|€ The secondary outcomes to be measured include the SARA and the Berg Balance Scale. These outcome measures will be performed once at baseline and again at week 3.

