## Study Procedures

- |€ Potential subjects will be referred to the primary investigator upon arrival to TIRR Memorial Hermann Inpatient or TIRR Memorial Hermann Kirby Glenn outpatient, or after their initial evaluation is performed. The evaluating physical therapist will contact the primary investigator if a patient is presenting with physical symptoms of cerebellar ataxia. The evaluating physical therapist will contact the primary investigator through a secure email and will email [[contact]](mailto:[contact]). The e-mail will include secure in the heading, protecting patient information and data.
- |€ Informed consent will be obtained prior to participation in this study. The principal investigator will introduce the study to potential participants at initial evaluation or during their first physical therapy treatment session. Patients will be given the informed consent document and will be allowed to ask questions regarding the purposes, confidentiality, and procedures of the study.
  - If consent is obtained, all consent forms will be collected in a locked cabinet at the primary investigatorâ€™s desk.
- |€ The Six Minute Walk Test, 10 Meter Walk Test, SARA, and BBS will be recorded at initial evaluation and will also be collected by the primary investigator.
- |€ Each individual patient will receive 30 minutes of the high intensity stepping intervention 3 times a week for 3 weeks. Therefore, each participant will receive 9 sessions of high intensity stepping training, for a total of 4 hours and 30 minutes by the studyâ€™s conclusion.
- |€ Each intervention will occur with either the primary investigator as the physical therapist or as another Doctor of Physical Therapy providing care for that patient. If another Doctor of Physical Therapy is providing care for that patient, they will be instructed by the primary investigator on where to put interventions, heart rate monitoring, and blood pressure monitoring in the note. As the intervention is not extremely specific and since it is considered standard of care for patients with stroke, brain injury, and spinal cord injury, the primary investigator will not be required to be the only therapist providing the intervention for this study.

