|€ The primary physical therapist will record all stepping interventions they performed in the treatment section of the note. The heart rate monitoring and heart rate data will be added in the treatment section of the note, below the actual treatment. Screen shots of the polar heart rate data for each patient will also be collected and stored in a coded file. Lastly, vitals before and after intervention will be recorded in the treatment section of the note under vitals.

|€ The 6 Minute Walk Test, 10 Meter Walk Test, SARA, and Berg Balance Scale will all be recorded again at discharge. There may also be additional walking measures weekly, depending on therapist preference, but physical performance measures will not count as a high intensity stepping intervention.

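### Optional weekly walking measures do not exclude the two primary walk tests, so uneven test practice could be counted as training gain

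*Combined protocol and SAP*

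**What the plan says.** Study Design names the outcomes: "The primary outcomes measured include the 10 Meter Walk Test and the 6 Minute Walk Test". It gives their timing as follows: "These outcome measures will be performed once at baseline and again at week 3". No section of the supplied text gives a practice walk, a number of trials per visit, or a rule for taking the best or the mean of several trials.

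Study Procedures says that the four measures "will be recorded at initial evaluation and will also be collected by the primary investigator". For the end of the study it says: "The 6 Minute Walk Test, 10 Meter Walk Test, SARA, and Berg Balance Scale will all be recorded again at discharge". The next sentence opens with "There may also be additional walking measures weekly, depending on therapist preference" and closes with the only limit placed on these measures: "physical performance measures will not count as a high intensity stepping intervention". They are not named, capped, standardised or carried into the analysis.

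On who delivers treatment, Study Procedures says: "Each intervention will occur with either the primary investigator as the physical therapist or as another Doctor of Physical Therapy". On design, Study Design says: "The study will be a non-blinded prospective case series performed at TIRR Memorial Hermann and TIRR Kirby Glenn". The Statistics section compares pre and post values with a paired t-test, plans MANOVAs to compare diagnosis groups, and sets the sample at 15. Quality control and assurance reserves the initial and final measures to the principal investigator.

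**The concern.** A patient who repeats a timed walk may do better because the course and the pacing are familiar. With a control arm on the same test schedule, that gain would largely cancel. Here there is no control arm, so it falls inside the estimated change and cannot be told apart from the effect of stepping training.

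The optional weekly measures make this uneven. One patient may reach the final test having walked the course only at baseline, while another may have repeated it in between because a particular therapist prefers weekly testing. Several therapists may treat, across an inpatient unit and an outpatient clinic, so retesting could follow site. Site could in turn follow diagnosis or chronicity. Practice could then enter the secondary comparison of response by diagnosis as well as the primary pre-post change.

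The plan keeps these tests out of the training dose but not out of the result. Having one assessor for the initial and final measures protects rater consistency; it does nothing about practice.

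**Working it through.** **Plan's own figure.** The sample size of 15 comes without effect size, SD, power, alpha or dropout, so there is nothing to reproduce. The calculation below shows only how sensitive the planned test is to practice.

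**Inputs.** From the documents: n = 15, one arm, paired t-test (Statistics; Study Design). Assumed: two-sided alpha 0.05, no true training effect, and a practice gain of d standard deviations of the change score. The documents give no value for d, so a range is shown.

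**Step 1: practice from baseline to final test only.** Degrees of freedom are 14 and the critical t is 2.145. An observed mean change of 2.145/√15 = 0.554 SD is therefore significant. The noncentrality parameter is d√15. The chance of p < 0.05 on one walk test is P(T > 2.145) + P(T < −2.145) under the noncentral t distribution:

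| d (assumed) | d√15 | upper tail | lower tail | chance of p < 0.05 |
|---|---|---|---|---|
| 0 | 0 | 0.0250 | 0.0250 | 5.0% |
| 0.1 | 0.387 | 0.0550 | 0.0101 | 6.5% |
| 0.2 | 0.775 | 0.1080 | 0.0036 | 11.2% |
| 0.3 | 1.162 | 0.1904 | 0.0012 | 19.2% |

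**Step 2: some patients also tested weekly.** Two further assumptions are needed: that the weekly measures are the primary tests, and that each prior test adds the same gain g. With the final test at week 3, a patient has 1 prior test (baseline) or 3 (baseline, weeks 1 and 2). If a share f is tested weekly, the mean gain is g(1 − f) + 3gf and the SD of change becomes √(1 + f(1 − f)(2g)²).

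| g | f = 0 | f = 0.5 | f = 1 |
|---|---|---|---|
| 0.1 | 6.5% | 11.1% | 19.2% |
| 0.2 | 11.2% | 29.4% | 58.0% |

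Example: g = 0.2 and f = 0.5 give a mean gain of 0.4 and an SD of 1.020, hence 29.4%.

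**Step 3: diagnosis comparison.** Suppose (again an assumption) groups of 8 and 7, with every patient in one tested weekly and none in the other. The groups then differ by 2g, the noncentrality is 2g/√(1/8 + 1/7), and there are 13 degrees of freedom. The false-positive rate is 6.5%, 11.1% and 18.9% for g = 0.1, 0.2 and 0.3.

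**Step 4: practice that levels off.** If all the gain comes with the first repeat, the weekly tests add nothing. Step 3 and the f = 0.5 and f = 1 columns of step 2 then fall away, and only the step 1 figures remain.

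**The case against.** The best reply is that much of the problem rests on inference.

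- **The weekly measures are unnamed.** They follow directly after a sentence naming the two walk tests, but they could be something else. This stands: the text permits repeats of the primary tests and does not state them.
- **Baseline may not be a first attempt.** A reader might infer a single, unpractised baseline. The word once may mean one occasion, and Study Procedures records the tests at initial evaluation and has the principal investigator collect them too. Referral may follow that evaluation, so some patients may already have walked. This stands, although it makes exposure less even.
- **Silence is not proof.** The study schedule and case report form are listed under Attachments but are not in the supplied text. This stands.
- **Practice need not affect everyone or always flatter the result.** Study Population admits some patients whose walk tests are recorded as 0 at the start, and they learn nothing about pacing from a walk not made. Background Information says motor learning is limited in this population. This stands.
- **The added walking is small.** Planned training is 9 × 30 = 270 minutes, and two extra 6 Minute Walk Tests add 12. That is true of dose, but the issue is familiarity with the test.
- **An uncontrolled case series already mixes recovery, usual therapy and practice.** This is also true, and standardising tests will not make the change attributable to training. Practice is, however, one contributor that can be reduced without adding an arm.

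**Conclusion.** The point holds as a gap in the measurement schedule. The plan lets therapists repeat the primary walk tests unevenly, describes no practice walk, and analyses the result in a way that would count any retest gain as training gain. It could also distort the diagnosis comparison if retesting follows site or diagnosis.

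The size is not known. At n = 15, an assumed two-sided 0.05 and no training effect, an assumed practice gain of 0.1 to 0.3 SD raises the chance of p < 0.05 on one walk test from 5.0% to between 6.5% and 19.2%. Anything beyond that from interim tests also requires that the weekly measures are the primary tests and that gains keep adding up.

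A reader might infer that every patient's change contains a practice gain, that it always favours the hypothesis, or that the number of attempts is bounded. The documents support none of these. The first two fail for the reasons given above. The last depends on a final test at week 3, whereas Study Procedures places it at discharge; a later discharge would leave room for more weekly tests.

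**What to change.** - **Study Procedures:** replace therapist preference with a rule that the 10 Meter and 6 Minute Walk Tests are not repeated between baseline and the final test. Other walking measures may still be used.
- **Study Design:** add one practice 10 Meter Walk before the recorded baseline, for patients able to walk.
- **Data collection:** record each patient's number of prior walk-test attempts, including any at the initial evaluation.
- **Reporting:** state that 6 Minute Walk practice cannot be separated from the training effect, since no practice trial is proposed for that test.
- **Final test time:** reconcile week 3 in Study Design with discharge in Study Procedures.

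Giving both tests to everyone at weeks 1 and 2 would even out exposure but is not a good alternative. If gains add linearly, each patient would carry three practice steps instead of one, and at g = 0.1 the false-positive rate would rise from 6.5% to 19.2%.

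The cost is small: a sentence or so in each section and one extra recorded item. Therapists lose discretion over interim use of these two tests, and the baseline visit is a few minutes longer.
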